Incentives (Factor 2): We have been studying incentives for repeat testing since 2015.⁴ We have found that low-income persons respond better to insuring at-risk rewards with repeat behavior than they do to cash payment.⁵ For example, suppose for your first test you are given as an incentive that offers an 80% chance of winning \$52. You then are told you can guarantee winning this lottery by having a second COVID-19 test in 8-months. This is preferable to a \$10 cash payment (i.e., the cost of the insurance against losing an 80:20 bet on \$52) in 8-months. To low-income persons, delivering an attractive lottery incentive for baseline testing and then letting persons insure this lottery with repeat testing may better encourage retesting by giving peace-of-mind and relieving them of worrisome distractions about money that they may already face. We will construct two incentives for this factor: (i) a baseline incentive offering a 90% chance of \$60; (ii) a repeat financial incentive. For (ii) Group 1 receives insurance on winning the baseline incentive; Group 2 receives a lottery incentive offering a 1 in 25 chance of winning \$150. The expected reward for both Group 1 and 2 for having completed both baseline and retest is \$60 (i.e., program costs are the same). In prior work, we've shown that insuring against losing a lottery was more effective than cash payments in the cost of insurance. Here we explore if this also holds true against low-probability and high-reward lotteries for which people may be optimistic about winning.

Messaging and incentives may interact. For example, thinking about the safety of your family after a family-framed message may make insuring against losing a lottery more attractive than another risky lottery.

Testing in a Diverse Population: Sampling low-income populations is important for research on disparities, however, recruiting this population is challenging because they often lack consistent contact information, do not have internet access, and mistrust research. We will use a novel way of recruiting this population by partnering

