7.1 DISCONTINUATION OF STUDY INTERVENTION/EXPERIMENTAL MANIPULATION

Participants who decline testing initially will be offered an exit survey which will ask them for reasons for declining. We will longitudinally follow the initial cohort that completed baseline survey (including people who declined testing in wave 1) and offer an additional wave of testing 6 months after the first wave.

Participants can choose to withdraw from the study at any time, and this will be documented in their REDCap record. When a subject discontinues Wave 2 retesting but not from the study, remaining study procedures (data analysis) will be completed as indicated by the study protocol.

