9.1 STATISTICAL HYPOTHESES

The figure below provides a conceptual diagram for thinking about what factors may influence testing take-up and retesting. Testing take-up would depend on several factors, including prior beliefs about infection, health literacy, information networks, health conditions, demographics and socio-economics. We have the following hypothesis based on analysis of literature on testing for HIV and Hepatitis as well as preliminary analysis of data from our prior study:

Hypothesis 1: Those who believe that they have been infected in the past would be more likely agree to testing to confirm that they have antibodies and potential immunity; **Hypothesis 2:** People with poor health literacy will be less likely to agree to testing as they might find it daunting to understand what the test does and how to interpret results; **Hypothesis 3:** Those who are risk averse would be more likely to agree to testing as it reduces uncertainty about serostatus; **Hypothesis 4:** Those with preexisting health conditions would be more likely to agree to testing as they face higher risks from COVID-19 and thus have more to gain from learning serostatus; **Hypothesis 5:** Minorities and those in lower socio-

economic strata would be less likely to agree to testing due to fear of discrimination, lack of trust in health care/research, poor past experience, and perception of being at low risk of infection. We also generate hypotheses for facilitators to retesting (r) relative to those who take a first test **Hypothesis 1r:** Persons who practice low COVID-19 mitigation, exhibit risk-seeking and have high exposure risk may respond to a lottery retest incentive. **Hypothesis 2r:** Those persons with low income, unemployed, or have high stress or anxiety may respond most to insurance of incentives. **Hypothesis 3r:** Persons who are sero+ at baseline will be less likely to return for a retest. **Hypothesis 4r:** Lottery insurance and family messaging will induce higher retesting rates. Hypotheses 1-5 are covariates that may affect agreeing to the test. Hypotheses 1r and 2r refer to heterogeneity of treatment effects for retesting, while 3r and 4r are main effects on retesting.

Conceptual diagram

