$$\pi = \beta_0 + \beta_1 x_{ij} + \eta_j + \varepsilon_i \quad [3]$$

For Hypothesis 3r, we will use a simple mixed-effects logistic model, where $\pi = \ln\left(\frac{p}{1-p_i}\right)$, is the probability of Time 2 attendance by individual i in household j given they attended Time 1 testing; β_1 is seropositivity status at Time 1 (yes vs. no); and η_j is the random intercept for each household capturing household-level effects.

We will use two separate models for Hypothesis 4r.

$$\pi = \beta_0 + \beta_1 x_{ij} + \beta_2 x_{ij} + \beta_3 x_{ij} + \beta_4 x_{ij} + \beta_5 x_{ij} + \eta_j + \varepsilon_i \quad [4a]$$

Model 4a will assess the probability, $\pi = \ln\left(\frac{p}{1-p_i}\right)$, of testing attendance for individual i in household j , where β_1 is the main effect for testing time (reference = Time 1); β_2 is the main effect for Financial Incentives (reference = lottery condition); β_3 is the main effect for Messaging (reference = personal); β_4 is the interaction between testing time and Financial Incentives; β_5 is the interaction between testing time and Messaging; and η_j is the random intercept for each household.

$$\pi = \beta_0 + \beta_1 x_{ij} + \beta_2 x_{ij} + \beta_3 x_{ij} + \beta_4 x_{ij} + \beta_5 x_{ij} + \beta_6 x_{ij} + \beta_7 x_{ij} + \eta_j + \varepsilon_i \quad [4b]$$

Model 4b will assess the probability, $\pi = \ln\left(\frac{p}{1-p_i}\right)$, of testing attendance for individual i in household j , where β_1 is the main effect for testing time (reference = Time 1); β_2 through β_4 are the main effects for study arm (personal messaging and loss protection, family messaging and lottery, family messaging and loss protection), where personal messaging and lottery is the reference group; β_5 through β_7 are the interactions between study arm and testing time; and η_j is the random intercept for each household.

For Models 4a and 4b, we will use unrestricted random sampling to select 3,000 observations, 2,000 times, clustered by household to bootstrap 95% confidence intervals for probability differences. We

will test differences in effect sizes for Model 4a (β_4 vs. β_5) and 4b (β_5 vs. β_6 ; β_5 vs. β_7 ; β_6 vs. β_7) using equality of regression coefficients tests.⁶ We will also calculate the inverse of observed probabilities to derive the Number Needed to Intervene on (NNI), and calculate standard errors by taking the square root of $P * (1 - P)/N$.⁷

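### The Number Needed to Intervene is defined without a comparator, and its stated standard error fits neither 1/P nor a between-arm difference

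*Combined protocol and SAP*

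**What the plan says.** All of this is in Section 9.4.1 of the combined protocol and SAP, after Models 4a and 4b, unless another section is named.

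- **Point estimate.** The analysts will "calculate the inverse of observed probabilities to derive the Number Needed to Intervene on (NNI".
- **Standard error.** They will "calculate standard errors by taking the square root of" P(1−P)/N. Neither symbol is defined there or elsewhere. The reference cited for the sentence is, by its title, about numbers needed to treat with time-to-event outcomes; the outcome here is attendance, yes or no.
- **Interval for differences.** A separate sentence draws samples "clustered by household to bootstrap 95% confidence intervals for probability differences". Each of its 2,000 samples contains 3,000 observations. The NNI sentence does not refer to it.
- **Comparators exist in the models.** In Model 4a, β₂ "is the main effect for Financial Incentives (reference = lottery condition"), and the messaging reference is the personal message. Model 4b compares study arms, "where personal messaging and lottery is the reference group".
- **The incentive reference level is itself incentivised.** Section 4.1: "Group 2 receives a lottery incentive offering a 1 in 25 chance of winning" $150.
- **Who is counted.** Section 9.1 says "We also generate hypotheses for facilitators to retesting (r) relative to those who take a first test". Section 7.1 says "We will longitudinally follow the initial cohort that completed baseline survey (including people who declined testing in wave 1") and offers them the second wave.

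**The concern.** A reader expects a number needed to intervene to mean how many people must receive one strategy rather than another to gain one extra retest. That needs a difference between two probabilities. The text names only one probability, so every arm, including the reference arm, gets a finite value whether or not the intervention works.

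The standard error raises a second problem. √(P(1−P)/N) belongs to a single proportion from independent observations. It is not the standard error of an inverse or of a difference, and families are randomised as clusters with a very high assumed correlation.

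At stake is one derived summary, though it is the kind of number that a policy reader takes away. The Hypothesis 4r tests and the sample size do not use it.

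**Working it through.** The plan gives no numerical NNI or NNI standard error, so there is no figure to reproduce. The formulas are evaluated directly.

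**Inputs from Section 9.2:** 2,160 people in 540 families, a mean of 4 per family; randomisation clustered by family; intra-cluster correlation above 0.90 (0.90 used); expected difference of 10 percentage points.

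**Assumptions not in the plan:** all families of size 4; equal split, so 270 households or 1,080 people per factor level and 135 households per Model 4b arm; control retest rate c of 20%, 50% or 80%, with intervention rate t = c + 0.10.

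Design effect: 1 + (4−1)×0.90 = 3.7.

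**1. Literal reading: P is one arm's attendance probability.**
- With no effect at 50%: 1/0.50 = 2.0 in both arms.
- With a 10-point effect, 1/t is 1/0.30 = 3.3, 1/0.60 = 1.7 and 1/0.90 = 1.1, while 1/(t−c) = 1/0.10 = 10 each time. So 1/P follows the attendance level and not the effect.
- Standard error of P at 0.50: √(0.25/1,080) = 0.015 with N as people; √(0.25×3.7/1,080) = 0.029 allowing for clustering; √(0.25/270) = 0.030 with N as households. For P itself the formula is about right if N is households and √3.7 = 1.9 times too small if N is people.
- Standard error of 1/P, by the delta method SE(P)/P²: at P = 0.60 and N = 1,080 people, before clustering, √(0.24/1,080) = 0.0149, and 0.0149/0.36 = 0.041. The formula gives 0.015.

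**2. Difference reading: P is the between-level difference, 0.10.**
- Stated formula: √(0.09/1,080) = 0.0091 (people) or √(0.09/270) = 0.0183 (households), whatever the two rates are.
- Clustered standard error of the difference: √([c(1−c)+t(1−t)]×3.7/1,080).

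| Control vs intervention | Clustered SE | Ratio to formula, people | Ratio to formula, households |
|---|---|---|---|
| 20% vs 30% | 0.0356 | 3.9 | 1.95 |
| 50% vs 60% | 0.0410 | 4.5 | 2.2 |
| 80% vs 90% | 0.0293 | 3.2 | 1.6 |

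The number of households cancels from these ratios, so they also hold for the 180 households per arm in the Section 9.2 table.

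- At a difference of 0 the formula gives 0. At −0.02, P(1−P) = −0.02×1.02 = −0.0204, which has no real square root.
- *If* an interval were built from the formula at 50% vs 60%: 0.10 ± 1.96×0.0091 inverts to 8.5–12.2, and 0.10 ± 1.96×0.0183 inverts to 7.4–15.6. With the clustered standard error, 0.10 ± 1.96×0.0410 = 0.0197 to 0.1803, which inverts to 5.5–51.

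**3. A single Model 4b contrast at 50% vs 60%.** With 135 households (540 people) per arm, SE = √(0.49×3.7/540) = 0.058. The limits are −0.014 to 0.214. They include zero, so they do not invert to one NNI interval.

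**4. Can the planned bootstrap supply the interval?** Full size would be 540 households, 2,160 people or 4,320 person-times. A sample of 3,000 observations matches none of these. A bootstrap that resamples k households instead of 540 scales the interval width by about √(540/k), so approximate coverage is 2Φ(1.96√(540/k)) − 1:
- 3,000 person-times, k = 3,000/8 = 375: about 98%.
- 3,000 people, k = 3,000/4 = 750: about 90%.
- 3,000 households: about 59%.

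**5. Who is in the denominator?** Time 1 attendance is part of the outcome in Models 4a and 4b, so those models cannot be restricted to first-test takers as Section 9.1 words the retest hypotheses. Section 7.1 follows wave 1 decliners who completed the survey, but under Section 5.5 only the head of household completes it, and under Section 8.1 individual study IDs go to members interested in testing. The documents do not show that other members who stayed away are all recorded.

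**The case against.** The best defence is that each reading leaves something correct. Read literally, 1/P is a legitimate count of people approached per attendee, P(1−P)/N is the right variance for P when N is households, and per-arm values side by side would show which arm did better. Read as a difference, the point estimate is right. The plan never says what the standard errors are for or that an NNI interval comes from them; the only interval method that it states is the household-clustered bootstrap for differences. Both factors compare two active conditions, so even 1/(difference) is not a number needed against doing nothing.

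Much of this stands, and it rules out three stronger inferences:

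- A reader might infer that the trial will publish NNI intervals several times too narrow. The documents do not say so; the 8.5–12.2 and 7.4–15.6 intervals are conditional on that use.
- A reader might infer that the benefit will be overstated 3-, 6- or 9-fold, from 10 divided by 3.3, 1.7 and 1.1. Those ratios compare two different quantities at assumed control rates, and mislead only if one is taken for the other.
- A reader might infer from the cited title that a difference was certainly meant. A title only suggests it.

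The defence does not rescue the sentence as a whole. On neither reading do the label, the estimate and the standard error fit together, and nothing elsewhere settles which reading applies.

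**Conclusion.** The specification is wrong as written, and the point is minor. As stated, the NNI is not an intervention effect: it is finite in every arm and equals 2.0 in both when there is no effect at an assumed 50% rate. The formula is not the standard error of 1/P (0.015 against 0.041 at P = 0.60 with 1,080 independent people). Nor is it that of a difference: it is 3.2 to 4.5 times too small for people or 1.6 to 2.2 times for households, and undefined for a negative difference.

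The size of the discrepancy rests on the assumed control rates of 20 to 80%, families of four and a correlation of exactly 0.90. The absence of a comparator, the mismatch of the formula and its failure for negative differences do not depend on those assumptions.

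**What to change.** Replace the NNI sentence in Section 9.4.1 with text that does the following:

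- Define NNI = 1/(Time 2 attendance probability at the intervention level minus that at the reference level already named in Model 4a or 4b). Say that it describes the Time 2 difference, not the time-by-arm interactions.
- Use the same individuals that those models analyse, and state who is enumerated in that denominator. Do not assume that non-attending members other than the head of household are all recorded.
- Delete √(P(1−P)/N) as the NNI's standard error.
- Take the interval by inverting the limits of a household-clustered bootstrap of that difference, resampling as many whole households as were randomised in place of a fixed 3,000 observations.
- When the limits include zero, report the difference with its interval instead of an NNI interval.
- If people approached per attendee is also wanted, report 1/P per arm under another name.

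The cost is a short paragraph of SAP text and a check of which household members are on record. The downside is that the reported NNI will be larger than 1/P, with a wider interval, and some Model 4b contrasts may have no reportable NNI interval.

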9.2 SAMPLE SIZE DETERMINATION

We will recruit a cohort of 2,160 people (540 families), and stratify into 3 subgroups based on predictors of commitment to participation in testing programs. Randomization will be clustered by family. Sub-group membership will be based on the mean household survey response to the survey component. For the purposes of power analyses, we assume high Intra Cluster Correlation within family on uptake of repeat testing (>0.90).

Stratified Allocation Plan and Power Analysis (540 households, 2160 individuals)		
	Control	Intervention
Stratification	# households	# households
HTE Subgroup 1	60	60
HTE Subgroup 2	60	60

HTE Subgroup 3	60	60
% Seropositive in Baseline Test	10%	10%
Total Households Per Arm	180	180
Projected Average Treatment Effect Size	Reference Group	Reference+10%
Minimum Detectable Effect Size Compared to Controls (H4r)	±3%	
Detectable 3-subgroup HTE and Seropositivity (H1r, H2r, H3r)	±7%	

Assuming a similar effect size to prior studies in similar populations, we expect a 10 percentage point difference in repeat testing adherence between intervention and control groups. With 540 households, we are powered to detect as little as 3 percentage point difference between interventions and controls in the 540 households we will enroll. To assess heterogeneity of treatment effects (THE), there is more than 80% power to detect a between-subgroup difference of 7 percentage points, assuming 180 households in each sub-group.

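### The NNI standard error has no household term: if N counts individuals, it is about half the clustered value at the plan's own family size and ICC

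*Combined protocol and SAP*

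**What the plan says.** Section 9.4.1 (General Approach) fits two mixed logistic models for Hypothesis 4r, 4a and 4b. Both concern the probability "of testing attendance for individual i in household j", with a random intercept for the household. The closing paragraph of the section then does three things:

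- It plans a bootstrap "clustered by household to bootstrap 95% confidence intervals for probability differences".
- It plans tests of equality between regression coefficients.
- It derives the NNI by inverting observed probabilities, and says it will "calculate standard errors by taking the square root of" P(1−P)/N.

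Neither P nor N is defined, and nothing carries the household clustering over to the NNI.

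Section 9.2 (Sample Size Determination) says "Randomization will be clustered by family", plans 2,160 people in 540 families, and for the power analysis states "we assume high Intra Cluster Correlation within family on uptake of repeat testing", putting the value above 0.90.

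**The concern.** The square root of P(1−P)/N is the standard error of a simple proportion from N independent observations. Members of one family share an allocation, and the plan itself expects their retesting decisions to be almost identical. If N counts people, the formula credits the data with far more information than they hold. The paragraph respects clustering for probability differences and drops it for the NNI.

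What is at stake is how the NNI is read. It puts the incentive and messaging results in a form that a policy reader can use directly. If its error bars are too short, arms that the data cannot separate may look distinct.

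**Working it through.** The plan gives a formula for the NNI standard error but no numerical value, so there is no figure to reproduce. The check compares the formula with its clustered counterpart.

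**Inputs**

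- Mean family size m = 2,160 / 540 = 4 (Section 9.2).
- ICC: above 0.90 for repeat testing (Section 9.2), taken as 0.90 to 1.00; lower values are tried as a sensitivity check.
- Smallest family: 2, since Section 5.5 requires at least one adult and one child.
- P: not given. P = 0.5 is assumed for the example. The ratio of standard errors does not depend on P.
- Equal family sizes are assumed.

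**Standard error of a single-arm P, with N counting individuals**

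Design effect = 1 + (m − 1) × ICC. Stated SE / clustered SE = 1 / √(design effect).

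| m | ICC | Design effect | Stated / clustered SE |
|---|---|---|---|
| 4 | 0.90 | 1 + 3 × 0.90 = 3.70 | 0.52 |
| 4 | 0.95 | 3.85 | 0.51 |
| 4 | 1.00 | 4.00 | 0.50 |
| 4 | 0.50 | 2.50 | 0.63 |
| 4 | 0.30 | 1.90 | 0.73 |
| 3 | 0.90 | 2.80 | 0.60 |
| 2 | 0.90 | 1.90 | 0.73 |

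**Example on the NNI scale**

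Take 540 / 4 = 135 households, or 540 people, in each of the four factorial cells. This is an assumption, because the Section 9.2 table prints 180 households per arm. The ratio is the same either way.

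- Stated SE = √(0.5 × 0.5 / 540) = 0.0215. Limits for P are 0.458 to 0.542, so 1/P runs from 1.84 to 2.18 (width 0.34).
- Clustered SE = 0.0215 × √3.7 = 0.0414. Limits for P are 0.419 to 0.581, so 1/P runs from 1.72 to 2.39 (width 0.67).
- If 95% limits were formed from the stated SE, their coverage would be about 2Φ(1.96 / 1.92) − 1 = 0.69.

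**Simulation.** One arm of 135 families of four was simulated 20,000 times with P = 0.5. At ICC 0.90 the empirical SE was 0.0416 against 0.0215 from the formula, a ratio of 0.52, and coverage was 0.69. At ICC 0.95 the ratio was 0.51 and coverage was 0.67.

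**Other readings of the formula**

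- *N counts households.* The stated SE becomes √4 / √3.7 = 1.04 times the clustered SE at ICC 0.90, so it is about 4% too wide.
- *The formula is used directly as the SE of 1/P.* The delta method gives SE(1/P) = SE(P) / P². At P = 0.5 the clustered value is 0.0414 / 0.25 = 0.166, and 0.0215 is 13% of that.
- *P is a between-arm difference.* Assume 50% v 60% with 1,080 people per factor level. The formula gives √(0.1 × 0.9 / 2,160) = 0.0065. The clustered SE of the difference is √((0.25 + 0.24) / 1,080) × √3.7 = 0.041. The formula gives 16% of that.

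**The case against.** The strongest objection is that N is undefined. Models 1 and 2 in Section 9.4.1 analyse heads of household, one per family, and with a household N the formula is close to right. This stands as a reason to state the condition. It does not remove the point: the NNI sentence directly follows the individual-level Models 4a and 4b, no text says that N is households, and the plan needs a definition on either reading.

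A reader might infer that NNI error bars will be half their correct width whatever happens. The documents do not support that. The ICC above 0.90 is a power-analysis assumption about repeat testing only, whereas Models 4a and 4b also cover Time 1 attendance. Four is a planned mean, and families of two qualify. The factor also applies only to a single-arm proportion whose limits are inverted, a step the plan does not describe.

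A reader might also infer that the trial's comparison of arms is compromised, or that the plan contains NNI intervals with 69% coverage. Neither follows. The plan states standard errors for the NNI, and no NNI intervals or comparisons. The 69% describes limits built here to show the size of the problem. The arms are compared through models with a household intercept and through household-clustered bootstrap intervals for probability differences.

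**Conclusion.** The point holds in conditional form. The formula has no household term and leaves P and N undefined. If N counts individuals and P is a single-arm proportion, the stated SE is 0.50 to 0.52 of the clustered SE at four people per family and ICC 0.90 or more. It is about 0.63 to 0.73 if the ICC is 0.5 to 0.3, or about 0.73 for families of two at ICC 0.90. These figures assume equal family sizes. Apart from clustering, the formula is the SE of one proportion, not of 1/P or of a difference; on those readings the shortfall is larger in the examples worked. The defect is confined to a supplementary summary. It should be corrected, but no planned hypothesis test depends on it.

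**What to change.** Replace the standard-error rule in Section 9.4.1 with wording that does the following:

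1. Define P (a single-arm probability or a between-arm difference, and at which testing time) and N.
2. Obtain limits for P, or for the probability difference, by resampling whole households, drawing as many households as are in the data.
3. Invert those limits to the NNI scale.
4. If the limits of a difference include zero, report the NNI interval as passing through infinity.

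Step 2 should not simply borrow the planned draw of 3,000 observations. If all 2,160 people contribute both testing times there are 4,320 rows, and drawing 3,000 would inflate standard errors by about √(4,320 / 3,000) = 1.2.

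Steps 3 and 4 are preferable to percentiles of the reciprocal, which fail when resampled differences cross zero. With an assumed 50% v 60%, 135 households per arm and ICC 0.90, the clustered SE of the difference is √(0.49 / 540) × √3.7 = 0.058. About Φ(−0.10 / 0.058) = 4% of resampled differences would then be negative.

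The cost is one or two sentences of SAP wording and wider NNI error bars. No new data are needed, and the design and sample size do not change.
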